4.4 Secondary Endpoints Analysis

4.4.1 Secondary Estimands

The secondary endpoints of this study are:

- Change in BCVA (ETDRS letters) from Baseline at Month 18
- Change in photopic and/or mesopic macular sensitivity measured by microperimetry from Baseline at Month 18.

The following 5 attributes define the Secondary Estimand for change in BCVA from Baseline at Month 18:

1. Population: Participants with STGD1 that satisfy the inclusion/exclusion criteria specified in the protocol. The analysis will be performed in the ITT population.
2. Interventions: ACP versus Sham.
3. Variable: Change in BCVA from Baseline at Month 18.
4. Intercurrent events (ICE's) and strategies: Same as for Primary Estimand in Section 4.3.1.
5. Population-level summary: Mean difference between ACP group and Sham group in change from Baseline in BCVA at Month 18.

The following 5 attributes define the Secondary Estimand for change in photopic and/or mesopic macular sensitivity measured by microperimetry from Baseline at Month 18:

1. Population: Participants with STGD1 that satisfy the inclusion/exclusion criteria specified in the protocol and were enrolled at sites where microperimetry could be performed. The analysis will be performed in the subset of the ITT population with a baseline and at least one post-baseline microperimetry assessment.
2. Interventions: ACP versus Sham.

3. Variable: Change in photopic and/or mesopic macular sensitivity measured by microperimetry from Baseline at Month 18.
4. Intercurrent events (ICE's) and strategies: Same as for Primary Estimand in Section 4.3.1.
5. Population-level summary: Difference between ACP group and Sham group in mean change from Baseline in photopic and/or mesopic macular sensitivity measured by microperimetry at Month 18.

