#### **11.4.3 Statistical Analyses**

All statistical analyses will be conducted by the study Sponsor or under the authority of the study Sponsor. The Sponsor and the subjects will remain masked to treatments until the end of the study, except if safety considerations justify breaking the code for individual subjects.

Primary endpoint will be analyzed using a mixed model for repeated measures (MMRM) with all available data, using response variable of the area of ellipsoid zone defect measured by en face SD-OCT over time up to Month 18 including baseline and post-baseline assessments. The MMRM will be used to assess the difference between the treatment groups in terms of the rate of change (slope) in the area of ellipsoid zone defect from Baseline through Month 18. The fixed effects will include treatment group (avacincaptad pegol or Sham), time, pooled geographic region (North America or Rest of World) and treatment by time interaction. Subject is the random effect with repeated measures.

The efficacy analysis will be conducted on all randomized subjects according to the intention-to-treat principle.

A Statistical Analysis Plan (SAP) will provide the details for the statistical analyses.

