3.1 Intent-to-Treat Population

The Intent-to-Treat (ITT) population will include all participants who are randomized. Participants will be analyzed according to the treatment to which they have been assigned at the time of randomization regardless of the actual study drug the participant might receive during his/her participation in the study. The Intent-to-Treat (ITT) population will include all participants who are randomized. Participants will be analyzed according to the treatment that they have been assigned at the time of randomization regardless of the actual treatment that the participant received during his/her participation in the study. The ITT population will be used for the summary of demographics, baseline characteristics, participant disposition, and analyses of all efficacy endpoints.

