4.3.3 Supplementary Analysis: Jump to Reference Multiple Imputation

A supplementary analysis will be performed to estimate a slight modification of the Primary Estimand in Section 4.3.1, where instead of the hypothetical strategy, the treatment policy strategy is specified for the ICE of study drug discontinuation. To estimate this estimand, missing outcome data will be imputed using Jump to reference (J2R) multiple imputation (MI) under a missing not at random assumption. J2R MI will result in multiple data sets with complete outcome data. Then, the MMRM model described in Section 4.3.2 will be used to estimate the treatment effect in the multiple imputed data sets. Finally, Rubin's combination rules will be used to obtain a single estimate of the treatment effect and corresponding standard error.

It is worth noting that Rubin's rules can provide conservative inferences (Seaman et al. 2014, Bartlett 2021), e.g., CIs may have significantly greater than 95% coverage probability.

Therefore, jackknife resampling (Wolbers et al. 2022) may also be applied to obtain more accurate frequentist inferences.

The J2R assumption stipulates that the mean outcome trajectory in participants who discontinue study drug in the ACP group will follow the mean outcome trajectory of the Sham group, after the point of discontinuation. This J2R assumption will be used to impute missing outcome data for participants in the ACP group post study drug discontinuation. For participants in the Sham group at all time points and participants in the ACP group up to the time of study drug discontinuation, missing outcome data will be imputed under the missing at random assumption (MAR). The overall MI analysis will be implemented as follows:

1. Parameter estimation model: Let \mathbf{Y}_{Oi} denote the vector of all observed data, and \mathbf{Y}_{Mi} denote the vector of missing observations after the time point of the ICE (denoted by D_i), for participant i .
 - 1) Fit a multivariate normal (MVN) model using \mathbf{Y}_{Oi} , assuming MAR, to data up to the occurrence of the ICE. The MVN model will include pooled geographic region, treatment group, visit (categorical variable), and treatment-visit interaction in the mean function and have a common unstructured variance-covariance matrix across treatment groups.
 - 2) Draw a mean vector and a covariance matrix from the posterior distribution of the fitted MVN model parameters.

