4.4.3 Supplementary Analysis: Jump to Reference Multiple Imputation

Similar supplementary analyses to that described in Section 4.3.3 will also be performed for both secondary endpoints. The imputation of missing observations will proceed as described in Section 4.3.3, with the exception that baseline value (i.e. BCVA or photopic and/or mesopic macular sensitivity) will also be included in the mean function of the imputation model. Additionally, following J2R MI, an analysis of covariance (ANCOVA) with treatment group, pooled geographic region and baseline value will be performed in each of the 100 imputed data sets for change in BCVA and photopic and/or mesopic macular sensitivity from Baseline at Month 18. Finally, Rubin's rules will be used to combine treatment effect and standard error estimates from applying ANCOVA to the 100 imputed data sets.

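### If the microperimetry analysis set carries over to the jump-to-reference analysis, discontinuers with no post-baseline reading are excluded and never imputed

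*SAP*

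**What the plan says.** SAP 4.4.1 gives the microperimetry estimand a target population of eligible participants at sites able to do the test. It then sets the analysis set: "The analysis will be performed in the subset of the ITT population with a baseline and at least one post-baseline microperimetry assessment". The BCVA estimand in the same section uses the ITT population without such a condition.

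SAP 4.4.3 extends J2R to this endpoint: "Similar supplementary analyses to that described in Section 4.3.3 will also be performed for both secondary endpoints". It names no analysis set. It states two differences from 4.3.3. The baseline value "will also be included in the mean function of the imputation model", and Month 18 is analysed by ANCOVA in each of the 100 imputed data sets.

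SAP 4.3.3 describes its estimand as the primary one with a single change, "where instead of the hypothetical strategy, the treatment policy strategy is specified for the ICE of study drug discontinuation". On who receives the J2R assumption it says: "This J2R assumption will be used to impute missing outcome data for participants in the ACP group post study drug discontinuation". All other missing values are imputed as missing at random (MAR).

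Two general statements point the other way. SAP 3.1: "The ITT population will be used for the summary of demographics, baseline characteristics, participant disposition, and analyses of all efficacy endpoints". Protocol 11.4.3: "The efficacy analysis will be conducted on all randomized subjects according to the intention-to-treat principle".

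**The concern.** A treatment-policy analysis is meant to keep participants who stop drug and to account for what happens to them afterwards. Under J2R, an ACP participant who stops before the first post-baseline test follows the Sham mean at every later visit, and so contributes no benefit. The requirement for a post-baseline value removes such a participant before imputation if no later reading exists. Membership of the set then depends on something that happens after randomisation.

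The target population in 4.4.1 contains no such condition, and the imputation does not need it, because a participant with only a baseline value can be imputed from the model in 4.4.3. What is at stake is whether the robustness check on the microperimetry result reflects the discontinuers with the least follow-up.

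**Working it through.** The documents state no figure for this point, so there is none to reproduce. The check traces the text and then works out the size algebraically.

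**Step 1. Who lacks a post-baseline value.** The protocol's Schedule of Assessments places microperimetry at Screening, Month 9 and Month 18/Early Withdrawal, as an optional test. Protocol 10.3 asks for Early Withdrawal assessments from everyone who withdraws. SAP 4.10.1 assigns readings on days 2 to 411 to Month 9 and later ones to Month 18. For participants with a baseline value:

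| Participant | In the 4.4.1 set? | Treatment under J2R |
|---|---|---|
| Stops drug early but has a Month 9 reading | Yes | Month 18 imputed if missing |
| Leaves before Month 9 with an Early Withdrawal reading | Yes (windowed to Month 9) | Month 18 imputed |
| Stops before Month 9, no Early Withdrawal or other post-baseline reading | No | Never imputed |
| Stays on drug, test not done at either visit | No | Never imputed; would have been imputed under MAR |

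The third row is the point.

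**Step 2. What imputation would have given.** An ACP participant in the third row would receive the Sham mean at both visits, so a zero difference in expectation. One in the fourth row would receive the ACP mean. Sham participants receive the Sham mean in either case.

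**Step 3. Size.** All shares are of ACP participants with a baseline value, and all are assumed because the documents give none:
- d: on-treatment difference at Month 18
- q: stopped drug, no post-baseline reading
- m: still on drug, no post-baseline reading
- b: stopped drug, one post-baseline value, Month 18 missing

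J2R in everyone with a baseline: d(1 - q - b).

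J2R in the 4.4.1 set: d(1 - q - m - b)/(1 - q - m).

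With m = 0, the second divided by the first is 1/(1 - q), an excess of q/(1 - q):
- q = 5%: 0.05/0.95 = 5.3%
- q = 10%: 0.10/0.90 = 11.1%

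Example with q = b = 10%, m = 0 and d = 0.50 SD: 0.50 × 0.80 = 0.400 SD in everyone with a baseline, against 0.50 × 0.80/0.90 = 0.444 SD in the 4.4.1 set. A large simulated sample with these shares gave 0.397 and 0.441 SD.

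**Step 4. Excluded participants still on drug.** With q = 10%, m = 5% and b = 10%, the ratio is (0.75/0.85)/0.80 = 1.103. The excess is 10.3%, below the 11.1% from q/(1 - q). If the whole baseline-only share of 15% were put in for q, the formula would give 0.15/0.85 = 17.6%, which is too much. So q must count discontinuers only, and q/(1 - q) is then an upper bound.

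**Step 5. The tested analysis.** The response in SAP 4.4.2 is change from baseline at post-baseline visits. A participant with no post-baseline value supplies no response to that model, whether in the set or not.

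**The case against.** The strongest objection is that the restricted set may not apply to 4.4.3 at all. That section names no set, and SAP 3.1 assigns ITT to every efficacy endpoint. This stands in part, since the carry-over is inferred. It is still the natural reading, because 4.4.1 is specific to this endpoint and 4.3.3 changes only the discontinuation strategy. A programmer could defend either set, so the passages need reconciling in any case.

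Four stronger readings are tempting, and the documents do not support them.

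- **All early leavers are lost.** They are not. Anyone with an Early Withdrawal or Month 9 reading stays in. The protocol asks for withdrawal assessments, so the excluded group may be small; because the test is optional, its size cannot be known in advance.
- **The estimate always flatters ACP.** That requires an on-treatment difference in ACP's favour. If the difference were adverse, leaving out participants imputed at zero effect would make ACP look worse. The excess is also relative to the J2R assumption, not to an observed treatment-policy effect.
- **The confirmatory comparison is compromised.** Step 5 shows that the set rule does not alter the main MMRM.
- **Microperimetry should have had the same population as BCVA.** A separate population is reasonable for an optional, equipment-dependent test with two post-baseline timepoints. Only the post-baseline clause is open to question.

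**Conclusion.** The point holds in a narrow form. As the SAP is most naturally read, the J2R analysis of microperimetry excludes participants who stop drug before Month 9 and have no post-baseline reading, and so never imputes them. When the on-treatment difference favours ACP, the supplementary estimate is too large by up to about 5% to 11% for an assumed q of 5% to 10%.

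This rests on three assumptions: the 4.4.1 set carries over to 4.4.3; q, which the documents do not give, lies in that range; and retained discontinuers' observed values centre on the ACP mean. A larger q would give a larger excess, but nothing in the documents supports one.

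The consequence is minor. The analysis is supplementary, and its endpoint is the last in the fixed sequence of SAP 2.1, formally tested only if the primary endpoint and BCVA both succeed.

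**What to change.** In SAP 4.4.3, define the microperimetry J2R set as all randomised participants with a baseline microperimetry value, analysed as randomised. The baseline test is done at Screening, before randomisation, so this condition does not depend on later events. Reconcile 4.4.1 with it, and note in 3.1 that microperimetry is an exception to full ITT because baseline is not available for everyone. Report by arm how many participants have a baseline but no post-baseline value, split by whether they had stopped drug, so that q can be seen.

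The cost is about one sentence in 4.4.3, matching edits in 4.4.1 and 3.1, and one line in a table. No new data are needed and the main MMRM test does not change. The downside is that the supplementary estimate may be slightly less favourable.

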4.4.2 Main Analytical Approach

For analyses of both secondary endpoints, the treatment effect will be estimated using MMRM with the following fixed effects: treatment group (ACP or Sham), visit (categorical variable), pooled geographic region (North America or Rest of World), treatment by visit interaction and baseline value of BCVA or photopic and/or mesopic macular sensitivity. The response variable will be the change from Baseline in BCVA or photopic and/or mesopic macular sensitivity measured by microperimetry at each scheduled post-baseline visit through Month 18. An unstructured (co)variance structure will be used to model the within-participant errors. The model will be fitted using REML estimation. If this analysis fails to converge, alternative correlation structures (e.g., heterogeneous autoregressive or heterogeneous compound symmetry, in this order) will be considered. The Kenward-Roger approximation will be used to estimate denominator degrees of freedom.

Statistical testing of the mean difference in change from Baseline in BCVA between ACP group and Sham group (defined as ACP minus Sham) at Month 18 from the MMRM will be performed at a 2-sided significance level of 5% only if the null hypothesis for the primary efficacy endpoint is rejected. The statistical testing of the difference for mean change from Baseline in photopic and/or mesopic macular sensitivity measured by microperimetry will be performed at a 2-sided significance level of 5% only if the null hypothesis for the primary efficacy endpoint and the secondary endpoint of change in BCVA at Month 18 are rejected, according to the fixed sequence procedure specified in Section 2.1.

4.4.3 Supplementary Analysis: Jump to Reference Multiple Imputation

Similar supplementary analyses to that described in Section 4.3.3 will also be performed for both secondary endpoints. The imputation of missing observations will proceed as described in Section 4.3.3, with the exception that baseline value (i.e. BCVA or photopic and/or mesopic macular sensitivity) will also be included in the mean function of the imputation model. Additionally, following J2R MI, an analysis of covariance (ANCOVA) with treatment group, pooled geographic region and baseline value will be performed in each of the 100 imputed data sets for change in BCVA and photopic and/or mesopic macular sensitivity from Baseline at Month 18. Finally, Rubin's rules will be used to combine treatment effect and standard error estimates from applying ANCOVA to the 100 imputed data sets.

4.4.4 Sensitivity Analysis: Re-Randomization Test

The same rerandomization test, as described in Section 4.3.4 will be performed for both secondary endpoints, with the exception that the 2-sided re-randomization p-value is calculated as: $p = 2 \times P(t_i \geq t^* | H_0) = \frac{\sum_{i=1}^{1000} I\{t_i \geq t^*\}}{1000}$, where $I(\cdot)$ is an indicator function. If $p > 1$, the re-randomization p-value will be set to 1. The difference in the calculation of the p-value is required to reflect that positive values of the test statistic for the secondary endpoints indicate favorable results for ACP, unlike for the primary endpoint.

4.5 Supportive Endpoint(s) Analysis

The supportive endpoints are:

- Rate of change in the area of atrophic lesion (DDAF) measured by FAF from Baseline through Month 18
- Rate of change in the thickness of the outer nuclear layer measured by a horizontal scan through the foveal center using SD-OCT from Baseline through Month 18
- Rate of change in the square root transformed area of ellipsoid zone defect measured by en face SD-OCT from Baseline through Month 18
- Time to persistent vision loss (defined as BCVA loss ≥ 10 , 15 or 20 letters from Baseline at two or more consecutive visits through Month 18).
- Emergence of at least one new atrophic lesion (DDAF) measured by FAF through Month 18.

The supportive endpoints of the rate of change in the area of atrophic lesion (DDAF) measured by FAF from Baseline through Month 18, the rate of change in the thickness of the outer nuclear layer measured by a horizontal scan through the foveal center using SD-OCT from Baseline through Month 18, and the rate of change in the square root transformed area of ellipsoid zone defect measured by en face SD-OCT from Baseline through Month 18 will be analyzed similarly to the primary endpoint using the analysis method in Section 4.3.2. The MMRM model will include all observed outcomes for these endpoints at each scheduled visit from Baseline through Month 18. Fixed effects will include treatment group (ACP or Sham), time, pooled geographic region (North America or Rest of World), and treatment by time interaction. The random effects will be at the participant-level. The model will be fitted using REML estimation with unstructured (co)variance matrix. Comparison between ACP group and Sham group will be performed at a 2-sided 0.05 significance level. The difference between ACP group and Sham group (ACP – Sham) in the treatment effect, and the associated standard error and 95% CI will be provided.

Time to persistent vision loss is defined for each participant as the first study day (in months) where the participant experiences a BCVA loss ≥ 10 , 15 or 20 letters from Baseline at two or more consecutive visits through Month 18. Participants without a vision loss event have their time to event censored at the last assessment of BCVA prior to the end of the study, or at 0.03285 months (i.e. day 1) if no post-baseline BCVA assessments are available. The hazard ratio for ACP vs. Sham on time to persistent vision loss, along with its corresponding 95% CI, will be calculated using a stratified Cox proportional hazards regression model with

pooled geographic region (North America or Rest of World) as the stratification factor. The two-sided p-value will be derived using the stratified log-rank test with pooled geographic region as the stratification factor. The 5th percentile and median time to the first occurrence of persistent vision loss will be analysed using the Kaplan-Meier method without stratification. Additionally, the event rate at Month 6, 9, 12, 15 and 18, and corresponding 95% CIs will be estimated using the Kaplan-Meier method without stratification and Greenwood formula with complementary log-log transformation.

For the emergence of at least one new atrophic lesion (DDAF) through Month 18, participants who do not have any atrophic lesion (DDAF) assessments through Month 18 will be excluded from the analysis. A dichotomized response (yes or no new atrophic lesion) will be evaluated and tested using Cochran-Mantel-Haenszel χ^2 test for risk difference between ACP and Sham adjusting for the stratification factor of pooled geographic region (North America or Rest of World). The odds ratio and its corresponding 95% CI will be reported for ACP vs. Sham.

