SYNOPSIS	
	
(ONL) measured by a horizontal scan through the foveal center using SD-OCT from Baseline through Month 18.
 
 
• Time to persistent vision loss (defined as BCVA loss <math>\geq</math> 10, 15 or 20 letters from Baseline at two or more consecutive visits through Month 18).
 
• Emergence of at least one new atrophic lesion (DDAF) measured by FAF through Month 18.
 
 
Safety Endpoints:
 
 
• Adverse events, vital signs, ophthalmic variables [ophthalmic examination, intraocular pressure (IOP), fluorescein angiogram (FA), FAF, SD-OCT, microperimetry], ECG and laboratory variables.
 

PLANNED SAMPLE SIZE:	Approximately 120 subjects will be enrolled in this study, 60 per dose group.
SUBJECT SELECTION:	Subjects of either gender, aged 18 – 60 years of age (inclusive), with the diagnosis of STGD1.
TEST DRUG DOSAGE:	Subjects randomized to avacincaptad pegol will receive 6 doses of avacincaptad pegol 2 mg and 15 doses of avacincaptad pegol 4 mg.

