## 7. PROCEDURES

Imaging assessments are collected at the timepoints specified in Section 10.2 “Trial Assessments”. The RC will analyze the data from three timepoints prior to database lock: Screening, Month 9 and Month 18. The additional imaging assessments collected at Month 3, Month 6, Month 12 and Month 15 will be stored and made available if needed.

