### 11.3.1 Determination of Sample Size and Statistical Rationale

Approximately 120 subjects will be enrolled in this study. This statistical rationale for the trial is based on the methodology presented in Fleming and Richardson (2004). Patients will be maintained on their randomized intervention (including those on the Sham control) for 18 months.

The primary analysis of this Phase 2b trial for the comparison of avacincaptad pegol vs the Sham is formally based on a three-category decision guideline. To be specific, if  $SD_{\Delta}$  is the standard deviation of the rate of change in the area of ellipsoid zone defect measured by en face SD-OCT over 18 months within each treatment group, the decision guideline for this trial is based on whether the difference between avacincaptad pegol and the Sham groups in the estimated mean rate of change in this area is less than  $0.1843 SD_{\Delta}$ , is from  $0.1843 SD_{\Delta}$  to  $0.3577 SD_{\Delta}$ , or is at least  $0.3577 SD_{\Delta}$ .

Note that these categories should not be interpreted as providing strict decision rules but rather as guidelines that will be factored into a broader scientific assessment of the benefit to risk profile of avacincaptad pegol. This broader assessment will include consideration of safety, of supportive efficacy endpoints, and of relevant information external to this trial. Specifically, the decision guidelines for this trial are:

1. If the difference between avacincaptad pegol and the Sham groups in the estimated mean rate of change in the area of ellipsoid zone defect measured by en face SD-OCT over 18 months is less than  $0.1843 SD_{\Delta}$ , then avacincaptad pegol is not plausibly more efficacious than the Sham.
2. If the difference between avacincaptad pegol and the Sham groups in the estimated mean rate of change in the area of ellipsoid zone defect measured by en face SD-OCT over 18 months is from  $0.1843 SD_{\Delta}$  to  $0.3577 SD_{\Delta}$ , then avacincaptad pegol is plausibly more efficacious than the Sham.
3. If the difference between avacincaptad pegol and the Sham groups in the estimated mean rate of change in the area of ellipsoid zone defect measured by en face SD-OCT over 18 months is at least  $0.3577 SD_{\Delta}$ , then this dose of avacincaptad pegol would be statistically significantly more effective than the Sham, with strength of evidence meeting the standard requirement of a 0.025 one-sided, false positive error rate.

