The planned size of 120 subjects for this phase 2b trial was determined based on the number of subjects with STGD1 that could potentially be enrolled within a reasonable

period of time. Based on the actual recruitment rate during the trial, this number may be increased or decreased. As STGD1 is an orphan indication, there is no natural history data currently available regarding the standard deviation of rate of change in the area of ellipsoid zone defect over 18 months in the STGD1 patient population that we plan to enroll in this trial.

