1.3 Randomization

Participants will be randomized in a 1:1 ratio to the following two treatment groups: ACP and Sham.

Participants will be centrally allocated to one of the two treatment groups by a dynamic minimization procedure (see Section 5.1 Appendix 1 for details). Randomization will be stratified by site and performed using an IRT system based on the stratification information to randomize each participant and assign a treatment group. Details of the randomization procedure can be found in Appendix 1.

All participants will be treated as follows:

Induction Phase: Administered starting on Day 1, 14 days apart for a total of 6 administrations (Day 1 – Month 2):

- ACP 2mg/eye or Sham

Maintenance Phase: Administered monthly (Month 3 – Month 17):

- ACP group continued with ACP 4 mg/eye (administered as two injections of ACP 2 mg)
- Sham group continued with Sham + Sham to maintain the masking

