4 STATISTICAL ANALYSES

4.1 General Considerations

Continuous data will be summarized descriptively including the number of participants (n), mean, standard deviation (SD), median, minimum, 1st quartile (Q1), 3rd quartile (Q3), and maximum. Categorical data will be summarized by frequencies and percentages. Percentages by categories will be based on the number of participants with no missing data, i.e., the percentages for the non-missing categories will add up to 100%.

All statistical comparisons will be conducted using 2-sided tests at the 5% significance level.

All data summarization and analyses will be performed using SAS® Version 9.4 and Enterprise Guide 7.15 HF8. Specifications for table, figures, and data listing formats can be found in the TLF specifications.

Baseline values will be defined as the last available value prior to the first dose of study drug. Unless otherwise specified, where multiple measurements are taken on the same day, the baseline value will be taken to be the average of the multiple measurements. Specifically:

- For BCVA, the baseline value will be taken as the average of the last two pre-treatment values for the study eye. This will typically be the Screening and Day 1 (D0) values. If there is only one pre-treatment value present, then this will be the baseline value. The baseline value for the fellow eye will be the last pre-treatment value. This will typically be the value at Screening.
- For area of ellipsoid zone defect, the baseline value will be the last pre-treatment value. This will typically be the measurement at Screening.
- For intraocular pressure (IOP), the baseline value will be taken as the average of the last two pre-treatment values for the study eye. This will typically be the Screening and Day 1 (D0) pre-injection values. If there is only one pre-treatment value present, then this will be the baseline value. The baseline value for the fellow eye will be the last pre-treatment value. This will typically be the value at Screening.

Change from baseline to post-baseline will be calculated as: post-baseline value – baseline value.

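### The new-lesion endpoint implicitly scores participants whose graded FAF ends early as having no new lesion through Month 18, which favours whichever arm has shorter follow-up

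*SAP*

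**What the plan says.** SAP Section 4.5 gives this endpoint one inclusion rule and one coding rule. Participants "who do not have any atrophic lesion (DDAF) assessments through Month 18 will be excluded from the analysis". For the rest, "A dichotomized response (yes or no new atrophic lesion) will be evaluated" by a CMH test for the risk difference, stratified by pooled geographic region, with an odds ratio reported. No minimum follow-up, Month 18 image requirement, censoring, imputation or sensitivity analysis is given. Under SAP Section 4.1, "All statistical comparisons will be conducted using 2-sided tests at the 5% significance level".

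On imaging, Protocol Section 7 states: "The RC will analyze the data from three timepoints prior to database lock: Screening, Month 9 and Month 18". FAF from Months 3, 6, 12 and 15 is stored for use if needed. Protocol Section 10.2.1 requires FAF at Screening, and Sections 10.2.24 and 10.3 call for it at Early Withdrawal. FAF appears in none of the window tables in SAP Section 4.10.1; the nine-month table covers SD-OCT, microperimetry, FP and FA.

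The neighbouring endpoint in SAP Section 4.5, time to persistent vision loss, is handled differently: participants without an event are censored at their last BCVA assessment.

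**The concern.** A yes/no outcome through Month 18 is fully known for two kinds of participant: those seen to develop a lesion, and those graded lesion-free at Month 18. Someone last graded at Month 9 without a lesion is in neither group, yet the coding puts that person beside participants observed for twice as long. The CMH test has no term for time at risk.

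The exclusion adds a wording problem. It refers to any DDAF assessment through Month 18, not any post-baseline assessment. Since Screening FAF is scheduled for everyone, the literal text would exclude almost nobody.

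Unequal follow-up is possible because the procedures differ. The ACP regimen is 6 single-injection doses plus 15 two-injection doses, 6 + 15 × 2 = 36 intravitreal injections, while sham uses a syringe without a needle (Protocol Sections 9.2.3 and 17.4). The documents do not establish that dropout differs. If it does, a spurious difference could enter the broader benefit-risk assessment in Protocol Section 11.3.1, which takes supportive efficacy endpoints into account.

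**Working it through.** **Inputs from the documents.** "Approximately 120 subjects will be enrolled in this study, 60 per dose group"; 1:1 allocation (SAP Section 1.3); two-sided 5% tests (SAP Section 4.1); reads at Screening, Month 9 and Month 18 (Protocol Section 7). The sample size "was determined based on the number of subjects with STGD1 that could potentially be enrolled", so the documents give no power, lesion risk or dropout figure for this endpoint. The one stated figure that can be reproduced belongs to the primary endpoint: 1.960 × √(2/60) = 0.3578 SD, against 0.3577 SD in Protocol Section 11.3.1. It confirms the arm size and the one-sided 0.025 level but does not bear on this point.

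**Assumptions.** No true effect, so both arms share the same risks: r9 by Month 9 and r18 by Month 18. A proportion d of each arm drops out before Month 18, unrelated to lesion risk.

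**Case A: every dropout has a Month 9 read.** Observed risk = (1 − d) × r18 + d × r9. The difference between arms is therefore −(d_ACP − d_Sham) × (r18 − r9), which is zero when dropout is equal.

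**Case B: half the dropouts have no post-baseline read and are excluded.** Observed risk = [(1 − d) × r18 + (d/2) × r9] / (1 − d/2).

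Worked example, 15%/30% and 20% v 10%:
- A: ACP 0.8 × 0.30 + 0.2 × 0.15 = 0.270; Sham 0.9 × 0.30 + 0.1 × 0.15 = 0.285; difference −1.5 points.
- B: ACP (0.240 + 0.015)/0.90 = 0.2833; Sham (0.270 + 0.0075)/0.95 = 0.2921; difference −0.9 points.

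| r9 / r18 | Dropout, ACP v Sham | Case A | Case B |
|---|---|---|---|
| 15% / 30% | 20% v 10% | 27.0% v 28.5%: −1.5 | 28.3% v 29.2%: −0.9 |
| 15% / 30% | 30% v 10% | 25.5% v 28.5%: −3.0 | 27.4% v 29.2%: −1.9 |
| 25% / 45% | 30% v 10% | 39.0% v 43.0%: −4.0 | 41.5% v 43.9%: −2.5 |

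Differences are in percentage points, from unrounded risks. Swapping the dropout rates between arms reverses every sign.

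**Effect on the test.** A second set of assumptions used a constant hazard (r9 = 1 − √(1 − r18)), r18 from 20% to 50%, 60 per arm and an unstratified chi-square by normal approximation. If 20% of ACP and 5% of Sham are last read at Month 9, the shift is −1.4 to −3.1 points and the null rejection rate 5.5% to 6.3%, against a nominal 5%. At 10% v 0% it is −0.9 to −2.1 points and 5.2% to 5.6%. If 10% of ACP and none of Sham lack any post-baseline image and are excluded, the shift is 0.0 and the rejection rate 5.0%.

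**Scale.** For the first table row, Case A, the standard error of the risk difference with 60 per arm is √(0.270 × 0.730/60 + 0.285 × 0.715/60) ≈ 0.082. A shift of 1.5 points is about 0.2 standard errors.

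**The case against.** A reader might infer that the SAP counts participants with no post-baseline imaging as lesion-free. The text does not support that as the plan's intent. The sentence before the coding rule excludes participants without DDAF assessments, and emergence of a new lesion cannot be judged from a baseline image alone. Most likely the qualifier post-baseline was left out. The same section uses it for BCVA, and SAP Section 4.4.1 uses it for microperimetry. Shifts computed by scoring Screening-only participants as lesion-free (−2.25, −4.5 and −6.5 points for the three rows, with half the dropouts Screening-only) depend on that literal reading and should not be cited as the expected size. The ambiguity should still be closed.

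A reader might also infer a bias toward ACP. The documents do not support this either: they give no dropout rates, and the sign reverses if Sham loses more participants.

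Three further objections carry weight. Early Withdrawal FAF should give most withdrawers a later image than Month 9, which would shrink the shifts above; but the plan does not say whether that image is graded, and it does not equalise time at risk. The endpoint is supportive and outside the fixed sequence in SAP Section 2.1, and Protocol Section 11.3.1 treats its decision categories as guidelines. DDAF area is also analysed with a slope model that uses time. These limit the importance of the point but leave the gap in the rule.

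**Conclusion.** The concern stands in a limited, conditional form. SAP Section 4.5 has no rule for participants whose graded FAF ends before Month 18 without a new lesion, and yes/no coding scores them as having none. Under no true effect this favours the arm with more or earlier dropout; if dropout is equal in amount and timing, there is no shift.

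In the illustrations tabulated, the shift is between −0.9 and −4.0 points when ACP loses more participants, and smaller if later withdrawal images are graded. All risks and dropout rates are assumed, and dropout is taken to be unrelated to lesion risk. This is a low-priority improvement that does not affect the primary or secondary conclusions.

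**What to change.** 1. Reword the exclusion in SAP Section 4.5 so that it applies to participants with no post-baseline DDAF assessment. State that this is a subset of the ITT population, since SAP Section 3.1 assigns all efficacy endpoints to ITT.
2. State that Early Withdrawal FAF is graded by the reading center, and add FAF to the window rules in SAP Section 4.10.1. The choice matters: if the nine-month windows were borrowed, an image from Day 412 (412/30.4375 ≈ 13.5 months) would be labelled Month 18.
3. Add an interval-censored complementary log-log model for time to first new lesion, with treatment and pooled region, over the intervals Screening to Month 9 and Month 9 to Month 18. Lesion-free participants are censored at their last graded FAF. A participant with no Month 9 read contributes one Screening-to-Month 18 interval, with event probability 1 − exp{−[exp(α₁) + exp(α₂)] × exp(βx)}, where α₁ and α₂ are the interval intercepts and βx is the linear predictor for treatment and region. The SAP should say how an off-schedule withdrawal image sets the end of its interval.
4. Keep the CMH proportion as a descriptive summary.

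The cost is a few lines of SAP text, one extra model, and any grading of withdrawal images not already planned. The effect becomes a hazard ratio reported beside the proportion, which is less direct to read. The model still assumes non-informative dropout, so it removes the problem of unequal follow-up but not that of selective dropout.
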